6.3 Camidanlumab Tesirine as Monotherapy Dosing

In the dose-escalation portion of the study (Part 1), the initial dose of camidanlumab tesirine will be 20 μ g/kg (Dose Level 1) every 3 weeks (Q3W), and the highest dose possibly tested will be 300 μ g/kg Q3W or equivalent (e.g., 100 μ g/kg every week). The dose-escalation procedure is described in Section 4.1.1.

A patient should maintain the same treatment schedule throughout the duration of the trial. However, once RDE is identified, patients receiving lower or higher dose levels of camidanlumab tesirine enrolled in Part 1 may be offered continued treatment at RDE.

Additional lower and/or intermediate dose levels to the provisional dose levels (Table 4) may be implemented. Dose level -1 may be used in case antitumor responses/significant toxicities are seen at Dose Level 1.

Table 4. Provisional Dose Levels in the Dose-Escalation (Part 1): Camidanlumab Tesirine as Monotherapy

Dose Level*	Dose of Cami
-1	10 µg/kg Q3W
1	20 µg/kg Q3W (starting dose)
2	30 µg/kg Q3W
3	45 µg/kg Q3W
4	60 µg/kg Q3W
5	80 µg/kg Q3W
6	100 µg/kg Q3W
7	125 µg/kg Q3W
8	150 µg/kg Q3W
9	200 µg/kg Q3W
10	250 µg/kg Q3W
11	300 µg/kg Q3W

* Additional or intermediate dose levels may be implemented during the study; however, the dose will not be higher than 300 µg/kg every 3 weeks (Q3W) or equivalent (e.g., 100 µg/kg every week [QW]).

Refer to Section 6.8 for premedication and supportive care.

6.4 Camidanlumab Tesirine Combination with Pembrolizumab Dosing

In the dose-escalation portion of the study (Part 1), the initial dose of camidanlumab tesirine will be 30 µg/kg (Dose Level 1) every 3 weeks (Q3W) for 2 cycles (on C1D1 and C2D1). The maximum dose possibly administered will be the highest dose of camidanlumab tesirine as monotherapy investigated and deemed to be safe. The dose-escalation procedure is described in Section 4.1.1.

Pembrolizumab at dose of 200 mg Q3W will be administered on Day 1 of each cycle starting from Cycle 1 onwards (dosing schedule 1).

If unacceptable toxicity (Section 6.5) occurs during Cycle 1 at dose level -1 and dose level -2, dosing Schedule 2, where pembrolizumab administration may start at Cycle 2, may be investigated in new enrolled patients.

Patients who tolerate the study treatment (i.e., no liver enzyme increase \geq Grade 2, no pleural effusion \geq Grade 2, no edema \geq Grade 2) and are in disease control (defined as disease control \geq SD) may receive additional doses of camidanlumab tesirine in combination with pembrolizumab, upon informing the Sponsor.

Additional administrations of camidanlumab tesirine in combination with pembrolizumab will be given as follows: 2 consecutive Cycles every 2 Cycles (2 cycles on, 2 cycles off schedule),

starting from Cycle 5 up to a year (i.e., Cycle 5 and 6, Cycle 9 and 10, Cycle 13 and 14, Cycle 17 and 18) if there is no delay in the planned treatment schedule: Between these cycles, patients should receive pembrolizumab as a single agent.

In case of delay in the administration of pembrolizumab, additional administrations of camidanlumab tesirine can be done after respecting a minimum of 63 days (9 weeks) between the last dose of camidanlumab tesirine and the first dose of the 2 subsequent additional administrations of camidanlumab tesirine.

Study treatment is given up to a year. Continued administration of camidanlumab tesirine as monotherapy or camidanlumab in combination with pembrolizumab, or pembrolizumab alone after a year is to be discussed with the Sponsor.

A patient should maintain the same treatment schedule throughout the duration of the trial. However, once RDE is identified, patients receiving lower or higher dose levels of camidanlumab tesirine enrolled in Part 1 may be offered continued treatment at RDE.

Additional lower and/or intermediate dose levels to the provisional dose levels ([Table 5](#)) may be implemented (no change in pembrolizumab dose).

If one study drug, camidanlumab tesirine or pembrolizumab, is put on hold or discontinued due to related toxicity, the other study drug could continue as single agent.

In the dose-expansion portion of the study (Part 2), patients will be assigned to the RDE of camidanlumab tesirine in combination with pembrolizumab recommended from Part 1. The RDE selected for Part 2 will be based on review of all available study data and will be recommended by the DESC.

Table 5. Provisional Dose Levels in the Dose-Escalation (Part 1): Camidanlumab Tesirine in Combination with Pembrolizumab

Dose Level*	Dose of Cami	Dose of pembrolizumab
-2	13 µg/kg Q3W × 2	200 mg Q3W
-1	20 µg/kg Q3W × 2	200 mg Q3W
1	30 µg/kg Q3W × 2 (starting dose)	200 mg Q3W
2	45 µg/kg Q3W × 2	200 mg Q3W
3	60 µg/kg Q3W × 2	200 mg Q3W
4	80 µg/kg Q3W × 2	200 mg Q3W
5	100 µg/kg Q3W × 2	200 mg Q3W
6	125 µg/kg Q3W × 2	200 mg Q3W
7	150 µg/kg Q3W × 2	200 mg Q3W
8	200 µg/kg Q3W × 2	200 mg Q3W
9	250 µg/kg Q3W × 2	200 mg Q3W
10	300 µg/kg Q3W × 2	200 mg Q3W

* Additional or intermediate dose levels may be implemented during the study; however, the dose will not be higher than the highest dose of camidanlumab tesirine as monotherapy every three weeks (Q3W) investigated and deemed safe.

6.5 Dose-Limiting Toxicities

For the dose-escalation of camidanlumab tesirine as monotherapy, a DLT is defined as any of the following events, which occur during the 21 days following the first study drug administration period of Part 1 (excluding the paired-biopsy cohorts), except those that are clearly due to underlying disease or extraneous causes.

For the dose-escalation of camidanlumab tesirine in combination with pembrolizumab, a DLT is defined as any of the following events, which occur during the 21 days following the first administration of pembrolizumab in Part 1, except those that are clearly due to underlying disease or extraneous causes.

A hematologic DLT is defined as:

Event	Severity
Febrile neutropenia or neutropenic infection	\geq Grade 3
Neutropenia lasting >7 days	\geq Grade 4
Thrombocytopenia	\geq Grade 4
Thrombocytopenia with clinically significant bleeding	\geq Grade 3
Thrombocytopenia requiring a platelet transfusion	\geq Grade 3
Anemia	\geq Grade 4
Anemia requiring transfusion	\geq Grade 3

A non-hematologic DLT is defined as:

Event	Severity
Hy's law case	Aspartate transaminase (AST) and/or alanine transaminase (ALT) $>3 \times$ upper limit normal (ULN) and bilirubin $>2 \times$ ULN, and without initial findings of cholestasis (serum alkaline phosphatase [ALP] activity $<2 \times$ ULN) and no other reason that could explain the combination of increased transaminases and serum total bilirubin, such as viral hepatitis A, B, or C, preexisting or acute liver disease, or another drug capable of causing the observed injury.
Hypersensitivity/infusion-related reaction (regardless of premedication)	\geq Grade 3. A Grade 3 hypersensitivity/infusion related reaction that resolves within 24 hours after onset with appropriate clinical management does not qualify as a DLT.
Radiculitis / Polyradiculopathy / GBS	\geq Grade 2
All other non-hematologic toxicity	\geq Grade 3

The following conditions **are not considered** DLTs:

Event	Severity
Fatigue	Grade 3 for \leq 7 days.
Diarrhea, nausea, or vomiting	Grade 3 in the absence of premedication that responds to therapy and improves by at least 1 grade within 3 days for Grade 3 events or to \leq Grade 1 within 7 days.
Alkaline phosphatase (ALP) and gamma glutamyl transferase (GGT)	Grade 3 ALP and GGT elevations, unless considered clinically relevant by the investigator.
Serum lipase or serum amylase	Grade 3 for \leq 7 days if without clinical signs or symptoms of pancreatitis.
Electrolyte abnormalities	Grade 3 that normalizes within 48 hours (with or without medical intervention) and does not manifest themselves clinically; in such instances, a follow-up sample MUST be taken within 48 hours to check whether such normalization has occurred.

A dose limiting toxicity is not a reason for treatment discontinuation.

Patients who experience a DLT that resolves or stabilizes with appropriate medical management may continue treatment at the discretion of the Investigator in consultation with the Sponsor.

6.6 Dose Delays and Modifications

When both camidanlumab tesirine and pembrolizumab have been dosed and an AE occurs with relationship to study treatment and requires study treatment hold, the resumption of study treatment can occur only with one study drug at a time. The second study drug may be resumed at the next planned Cycle.

In the above situation, prior to the resumption of any study drugs, discussion should occur with the Sponsor.

6.6.1 Dose Delays and Modifications for Camidanlumab Tesirine

The Investigator may suspend camidanlumab tesirine dosing for up to 21 days for any patient who experiences any toxicity of any grade.

Resumption of dosing with camidanlumab tesirine after any suspension, even when longer than 21 days, is at the discretion of the Investigator on assessment of the patient's clinical condition and whether or not the patient is deriving potential clinical benefit from treatment with camidanlumab tesirine.

Guidelines for management of toxicities, when considered to be at least possibly related to camidanlumab tesirine, are detailed:

- in Section 6.6.1.1 for general toxicities (i.e., not specified in the below sections),
- in Section 6.6.1.2 for specific non-hematologic toxicities,
- in Section 6.6.1.3 for specific hematologic toxicities,

- in Section [6.6.1.4](#) for specific neurologic toxicities,
- in Section [6.6.1.5](#) for specific skin toxicities.

When a patient is treated with the combination of camidanlumab tesirine and pembrolizumab, the management of irAEs related to camidanlumab tesirine will follow the recommendations for the management of irAEs related to pembrolizumab in [Table 14 \(Appendix 13.4\)](#).

6.6.1.1 Camidanlumab Tesirine Dose Modification Guidelines: General Toxicities

AE Grade	Camidanlumab Tesirine Management Guideline
1/2	No dose adjustment is required.
3/4	
First Occurrence:
 
Hold camidanlumab tesirine until improvement to \leqGrade 1 or Baseline.
 
If improvement to \leqGrade 1 or Baseline occurs prior to the next scheduled dose, continue camidanlumab tesirine at the original assigned dose level in subsequent treatment cycles.
 
If improvement to \leqGrade 1 or Baseline occurs >21 days from the last scheduled (but missed) camidanlumab tesirine dose, continue camidanlumab tesirine and reduce by 1 dose level from the original assigned dose in subsequent treatment cycles.
 
Second Occurrence:
 
Hold camidanlumab tesirine until improvement to \leqGrade 1 or Baseline.
 
If improvement to \leqGrade 1 or Baseline occurs prior to the next scheduled dose, reduce by 1 dose level from the original assigned dose in subsequent treatment cycles.
 
If improvement to \leqGrade 1 or Baseline occurs >21 days from the last scheduled (but missed) camidanlumab tesirine dose, continue camidanlumab tesirine and reduce by 2 dose levels from the original assigned dose in subsequent treatment cycles.
 
Otherwise, camidanlumab tesirine should be permanently discontinued.
 
Third Occurrence:
 
Permanently discontinue camidanlumab tesirine.

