4.2.2 Treatment Period

The treatment period starts on the date when a patient receives the first dose of study drug and continues until end of treatment visit.

A treatment cycle is defined as 3 weeks (i.e., 21 days).

After completion of Cycle 4, the Day 8 visit is not required unless clinically indicated.

Patients may continue treatment for up to 1 year or until disease progression, unacceptable toxicity, or other discontinuation criteria (Section 5.4), whichever occurs first. Additionally, patients benefiting clinically at 1 year may continue treatment after a case by case review with the Sponsor.

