AST, ALT, or GGT abnormalities or Edema or Effusion	2/3	
First Occurrence: Hold camidanlumab tesirine until improvement to \leqGrade 1 or Baseline.
 
If improvement to \leqGrade 1 or Baseline occurs prior to the next scheduled dose, continue camidanlumab tesirine at the original assigned dose level in subsequent treatment cycles.
 
If improvement to \leqGrade 1 or Baseline occurs >21 days from the last scheduled (but missed) camidanlumab tesirine dose, continue camidanlumab tesirine and reduce by 1 dose level from the original assigned dose in subsequent treatment cycles.
 
Second Occurrence: Hold camidanlumab tesirine until improvement to \leqGrade 1 or Baseline.
 
If improvement to \leqGrade 1 or Baseline occurs prior to the next scheduled dose, reduce by 1 dose level from the original assigned dose in subsequent treatment cycles.
 
If improvement to \leqGrade 1 or Baseline occurs >21 days from the last scheduled (but missed) camidanlumab tesirine dose, continue camidanlumab tesirine and reduce by 2 dose levels from the original assigned dose in subsequent treatment cycles.
 
Otherwise, camidanlumab tesirine should be permanently discontinued.
 
Third Occurrence: Permanently discontinue camidanlumab tesirine.

Adverse Event	Grade	Camidanlumab Tesirine Management Guideline
	4	
First Occurrence:
 
Hold camidanlumab tesirine until improvement to \leqGrade 1 or Baseline.
 
If improvement to \leqGrade 1 or Baseline occurs prior to the next scheduled dose, continue camidanlumab tesirine and reduce by 1 dose level from the original assigned dose in subsequent treatment cycles.
 
If improvement to \leqGrade 1 or Baseline occurs >21 days from the last scheduled (but missed) camidanlumab tesirine dose, continue camidanlumab tesirine and reduce by 2 dose levels from the original assigned dose in subsequent treatment cycles.
 
Otherwise, camidanlumab tesirine should be permanently discontinued.
 
Second Occurrence:
 
Permanently discontinue camidanlumab tesirine.

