	3	
Hold camidanlumab tesirine until improvement to \leqGrade 1 or Baseline and consider dermatology consult.
 
Topical treatment to affected areas is indicated and consider systemic corticosteroid treatment e.g., prednisone 0.5 mg/kg for 10 days:
 
 - maculopapular rash or photosensitivity rash: high potency topical steroid cream BID (e.g., clobetasol propionate 0.05%, halobetasol propionate 0.05%) and consider prednisone 0.5 mg/kg for 10 days. - pruritus: high potency topical steroid cream BID (e.g., clobetasol propionate 0.05%, halobetasol propionate 0.05%) and consider oral antipruritic (e.g., hydroxyzine, gabapentin, or pregabalin). - xerosis or hyperpigmentation: consider ammonium lactate 12% or urea 20% BID; and triamcinolone 0.1% cream BID. 
Reassessment every 2 weeks is indicated (either by healthcare professional or patient self-report); if reactions do not improve, then:
 
First Occurrence:
 
 • If improvement to \leqGrade 1 or Baseline occurs prior to the next scheduled dose, proceed with the originally planned camidanlumab tesirine dose level. • If improvement to \leqGrade 1 or Baseline occurs >21 days from the last scheduled (but missed) camidanlumab tesirine dose, reduce by 1 dose level from the original assigned dose in subsequent treatment cycles. 
Second Occurrence:
 
 • If improvement to \leqGrade 1 or Baseline occurs prior to the next scheduled dose, reduce by 1 dose level from the original assigned dose in subsequent treatment cycles. • If improvement to \leqGrade 1 or Baseline occurs >21 days from the last scheduled (but missed) camidanlumab tesirine dose, reduce by 2 dose levels from the original assigned dose in subsequent treatment cycles.

Adverse Event	Grade	Camidanlumab Tesirine Management Guideline

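### On the ordinary reading, recovery 0 to 21 days after a missed camidanlumab tesirine dose has no dose branch: 8 of 11 blocks discontinue it and 3 give no dose, while slower recovery continues at a reduced dose

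*Protocol*

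**What the plan says.** Protocol 6.6.1.1 deals with Grade 3/4 general toxicities. The drug is held until the event is back to Grade 1 or Baseline. At first occurrence, if recovery "occurs prior to the next scheduled dose, continue camidanlumab tesirine at the original assigned dose level". If it comes more than "21 days from the last scheduled (but missed) camidanlumab tesirine dose", the dose drops one level. At second occurrence the two actions are one level down and two levels down, and a closing line follows: "Otherwise, camidanlumab tesirine should be permanently discontinued".

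Protocol 6.6.1.2 repeats this structure for AST, ALT or GGT abnormalities, edema and effusion. In its more severe blocks the slow-recovery action is "continue camidanlumab tesirine and reduce by 2 dose levels from the original assigned dose in subsequent treatment cycles". Protocol 6.6.1.5 repeats it again for the rash group and for blistering rash. There, "Reassessment every 2 weeks is indicated", and the branches are introduced as what to do when the reaction has not improved.

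Protocol 6.6.1, which governs all these tables and calls them guidelines, says: "The Investigator may suspend camidanlumab tesirine dosing for up to 21 days for any patient who experiences any toxicity of any grade". It adds: "Resumption of dosing with camidanlumab tesirine after any suspension, even when longer than 21 days, is at the discretion of the Investigator", on the basis of clinical condition and potential benefit. It names no dose level. Protocol 6.6 adds that in combination patients held for a treatment-related event, the drugs restart one at a time and only after discussion with the Sponsor.

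**The concern.** The branches run in the wrong order. A patient who recovers ten days after a missed dose meets neither condition and, where the closing line is present, is discontinued. A patient with the same event who recovers on day 30 continues at a reduced dose. No rationale is given. The pembrolizumab rules in Protocol 6.6.2.1 run the expected way: a delay over 21 days prompts contact with the Sponsor, and a hold over 12 weeks ends treatment. The uncovered window is also the hold length that 6.6.1 itself foresees.

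At stake are the doses patients receive and the consistency of the descriptive dosing data. The frequency of dose interruptions and reductions is a primary endpoint (Protocol Section 3, Table 3), and relative dose intensity is summarized (SAP 4.7.1). SAP 4.3 also lists as important deviations a failure to withdraw study drug when mandatory discontinuation criteria are met, and a dose not specified in the protocol. A site that used its discretion to resume on day 10 could arguably be recorded under either.

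**Working it through.** **1. The window.** Let *d* be the day of improvement to Grade 1 or Baseline, counted from the missed dose (*d* < 0 means before the dose was due). The second branch calls the held dose the last scheduled one, now missed. The *next scheduled dose* in the first branch is therefore most naturally the upcoming dose.
- First branch: *d* < 0.
- Second branch: *d* > 21.
- Uncovered: 0 ≤ *d* ≤ 21, which is 21 − 0 + 1 = 22 calendar days.

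**2. Every block with two branches.** Entries that only discontinue (third occurrences, Grade 4 second occurrences) are left out. Numbers are dose levels below the assigned dose.

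| Section | Block | *d* < 0 | *d* = 0 to 21 | *d* > 21 |
|---|---|---|---|---|
| 6.6.1.1 | Grade 3/4, first | original | no dose given | −1 |
| 6.6.1.1 | Grade 3/4, second | −1 | discontinue | −2 |
| 6.6.1.2 | Liver enzymes/edema/effusion Grade 2/3, first | original | no dose given | −1 |
| 6.6.1.2 | same, second | −1 | discontinue | −2 |
| 6.6.1.2 | same, Grade 4, first | −1 | discontinue | −2 |
| 6.6.1.5 | Rash group Grade 3, first | original | no dose given | −1 |
| 6.6.1.5 | Rash group Grade 3, second (closing line falls after a page break) | −1 | discontinue | −2 |
| 6.6.1.5 | Rash group Grade 4, first | −1 | discontinue | −2 |
| 6.6.1.5 | Blistering Grade 2/3, first | original | discontinue | −1 |
| 6.6.1.5 | Blistering Grade 2/3, second | −1 | discontinue | −2 |
| 6.6.1.5 | Blistering Grade 4, first | −1 | discontinue | −2 |

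- Blocks: 2 + 3 + 3 + 3 = 11.
- Discontinue in the window: 1 + 2 + 2 + 3 = 8. Outside the skin tables this is 1 + 2 = 3 of 5; inside them, 2 + 3 = 5 of 6.
- No resumption dose: 11 − 8 = 3.
- After day 21 all 11 continue. Among the 8, seven continue at −2 and one at −1 (blistering Grade 2/3, first).

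**3. What the slower patient keeps.** From Protocol Table 5:
- Two levels down runs from 13/30 = 43.3% to 100/150 = 200/300 = 66.7% of the assigned dose.
- One level down runs from 13/20 = 65.0% to 125/150 = 250/300 = 83.3%.

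So, read literally, the day-30 patient continues at 43.3% to 66.7% in seven blocks and 65.0% to 83.3% in the eighth. The day-10 patient receives nothing further.

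**4. The other reading.** A cycle is 21 days (Protocol 4.2.2). If *next scheduled dose* means the slot after the missed one, the first branch covers *d* < 21, and only day 21 is uncovered. If it means the next camidanlumab tesirine dose, monotherapy gives the same result. In the combination, a missed Cycle 2 dose (target day 22, SAP Table 1) is followed by Cycle 5 (day 85), 63 days later. Days 22 to 62 (62 − 22 + 1 = 41 days) would then meet both branches, one level apart. That case is narrow.

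**5. Who can reach the window.** Monotherapy enrolment is complete (Protocol 1.3.4), so the forward effect lies mainly in the combination, where several rules thin it out:
- After a Cycle 2 dose, no camidanlumab tesirine is due for 85 − 22 = 63 days. On the ordinary reading, the first branch stays open for nine weeks.
- Protocol 6.4 makes doses from Cycle 5 optional and restricts them to patients without Grade 2 or higher liver enzyme increase, pleural effusion or edema. This largely empties the two discontinuing blocks of 6.6.1.2, apart from a delayed Cycle 2 dose.
- Protocol 6.6.1 sends immune-related events to Table 14, whose content was not available to check.
- Protocol 6.6.1.5.1 gives severe immune-mediated skin events their own rule, with Grade 4 discontinued whatever the recovery time.

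**The case against.** The strongest reply is that the tables are guidelines under an express discretion clause. Protocol 6.6.1 lets the Investigator resume after any suspension, and the closing line says *should* where the neurologic rules in 6.6.1.4 say *must*. For combination patients held for a related event, Sponsor discussion comes first, which limits divergence between sites. With 21-day cycles, the slot-after-the-missed-dose reading makes the branches meet except on day 21 and leaves the closing line for patients who never recover, which may be what was meant.

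A second reply concerns the skin tables, which hold five of the eight blocks. Their branches sit behind a condition that the reaction has not improved, so a patient who is better at a two-weekly reassessment may never enter them.

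Most of this stands as a limit on reach. A reader might infer that the protocol compels discontinuation of every patient who recovers within 21 days. The discretion clause and the Sponsor discussion do not support that. What they do not do is supply a dose level or remove the closing line, and the reading that closes the gap is nowhere stated. If the closing line means only failure to recover, days 0 to 21 have no dose in all 11 blocks on the ordinary reading. The skin lead-in is a further fault: it asks for non-improvement and then branches on improvement, so it neither clearly includes nor clearly excludes these patients.

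**Conclusion.** The defect is real on the text. On the ordinary reading of *next scheduled dose*, recovery on days 0 to 21 after a missed dose has no dose branch. Eight of 11 blocks then point to discontinuation and three give no resumption dose, while later recovery continues at −1 or −2 levels. On the alternative reading only day 21 is uncovered.

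Three further inferences are not supported. The 8 of 11 counts rule blocks, not patients. The documents give neither related-event rates in the combination nor recovery times, so frequency cannot be sized. DLT and MTD decisions are unaffected. Nor do the documents show that a patient whose event was unresolved on dosing day should return to the full assigned dose.

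The point ranks between minor and one that should be corrected. It is inexpensive to repair and bears mainly on combination dosing.

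**What to change.** In 6.6.1.1, 6.6.1.2 and 6.6.1.5, replace the more-than-21-days condition with wording that means recovery after the scheduled dose was missed. Any such recovery then takes the second-branch reduction already listed (−1 or −2 levels). Confine the closing discontinuation line to failure to return to Grade 1 or Baseline. Keep the Section 6.6.1 discretion for holds over 21 days and the existing last-occurrence discontinuations. In the skin tables, delete or reword the lead-in about reactions that do not improve.

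Check: *d* < 0 takes the first branch and *d* ≥ 0 the second in all 11 blocks, so no earlier recovery is treated more harshly than a later one.

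If the sponsor instead intended discontinuation for recovery after day 21, the condition should read 21 days or less, with Section 6.6.1 aligned and a closing line added to the three blocks that lack one. Either version removes the inversion.

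The cost is a wording amendment (Protocol 11.7), with no new data or visits. The downside is that some patients who recover within 21 days of a missed dose receive a lower dose than if they were given the first-branch dose: reduced instead of original in the four milder first-occurrence blocks, and −2 instead of −1 in the other seven.
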